# **RESEARCH PLAN**

### A. Specific Aims

**Hypothesis:** We hypothesize that two sessions of 10 days of RT-CGM in the setting of nutrition and physical activity counseling coupled with education on how exercise and nutrition affect blood sugar levels will promote weight loss in participants with prediabetes and diabetes and reduce glycemic variability.

**Aim 1**: Examine the effect of two 10-day sessions of RT-CGM over 6 weeks on weight loss, change in body composition, activity level and nutritional changes in subjects with diabetes and prediabetes 12 weeks later.

Aim 2: Evaluate participants' perception of RT-CGM as a weight loss tool.

**Aim 3**: Evaluate the effect of RT-CGM on glycemic variability in subjects with prediabetes and diabetes.

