### C. Preliminary Studies

Many studies have demonstrated that RT-CGM can be used in adults and children with both Type 1 and Type 2 diabetes resulting in improvement in HbA1c and/or a reduced frequency of hypoglycemia (17-19). Table 2 shows the average blood sugars of normal, prediabetic, and diabetic patients (24). Our initial research showed that the use of RT-CGM serially over 3 months improved HbA1c by an average of 1.0% in subjects with Type 2 diabetes on no prandial insulin (20). Nutrition and activity changes were not measured but the 3-month HbA1c improvement was sustained for another 9 months without further RT-CGM intervention (21). We hypothesized that the RT-CGM data motivated the subjects to make salutary changes in their diet and exercise habits leading to this long-term improvement in HgA1c (20, 21). However, there has been little direct examination of RT-CGM as a behavior modification/weight loss tool, as most studies have focused on HbA1c changes. Yoo et al. did show that intermittent use (3 days of RT- CGM every month for 12 weeks) produced a significant decrease in calorie

Page 2 of 14

consumption, increase in physical activity, improvement of weight, and a 1% decrease in HbA1c in poorly controlled patients with Type 2 diabetes (22). Allen et al. found that the data from a single three-day session of blinded CGM when combined with subsequent counseling and review of the CGM glucose data with the patient resulted in an increase in physical activity and a decrease in HbA1c by 1.2% and BMI by 0.5 kg/m^2 (23). The only study using RT-CGM in patients with prediabetes showed significant glycemic variability at baseline but did not show decreased glycemic variability or improvement in weight after 6 months, and diet and activity levels were not measured (24, 25). The reasons for the failure to achieve weight reduction in that study may have been due to the lack of specific lifestyle counseling and/or instructions on use/interpretation of RT-CGM to the subjects. In addition, the rigorous RT-CGM schedule in the protocol (6 days of RT-CGM wear on 4 occasions over 3 months) may have been too intense for patients with prediabetes who are generally not even required to perform fingerstick blood glucose measurements.

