In our original study on patients with Type 2 diabetes using RT-CGM, the mean, unadjusted HbA1c decreased by 1.0, 1.2, 0.8, and 0.8% in the RT-CGM group vs. 0.5, 0.5, 0.5, and 0.2% in the SMBG group at 12, 24, 38, and 52 weeks, respectively (P = 0.04). There was a significantly greater decline in HbA1c over the course of the study for the RT-CGM group than for the SMBG group, after adjusting for covariates (P < 0.0001, figure 1). Also, more people in the RT-CGM group experienced weight loss of >3 pounds in the 0- to 12-week time period compared with the SMBG group (P = 0.03, Table 1) (21). In the prediabetes study with RT-CGM significant glycemic variability (GV) was seen in prediabetes participants with Mean Amplitude of Glycemic Excursion: 50 +/- 18 mg/dL (24) as compared to other studies which showed excursions of 26-28 mg/dL in normal subjects and 75 +/- 28 mg/dL in patients with diabetes (31). However, the change in GV or weight loss was not significantly improved which was surprising as focus groups conducted after intervention were positive about the RT-CGM experience (25). Figure 2 is an example of a representative CGM tracing of a "normal" patient, a patient with prediabetes and one with diabetes. Behavior modifications were not evaluated in either the prediabetes or Type 2 diabetes RT-CGM study. The studies also did not assess whether blood sugars are affected by significant education about diet and exercise. We propose that further education on how to use RT-CGM will help facilitate weight loss and behavior modification. There are only two studies that have evaluated behavior modification changes in patients with Type 2 diabetes and none in the pre-diabetic population (see background above).

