#### Figure 1: Mean HbA1c change from Baseline

Change equals later HbA1c minus baseline HgA1c. This figure shows the raw mean changes and SEMs A separate multilevel model of the actual HbA1c values, with a transformation of the time variable to reflect the deceleration of change over time (1/time, with time defined as 1–5), showed that the decline in A1c over the course of the study differed between the groups net of other factors known to cause A1c change: age, sex, diabetes therapy, and initiation of insulin(21).

	0–12 weeks			0-52 weeks		
	RT-CGM	SMBG	Р	RT-CGM	SMBG	Р
Weight loss (> $-3$ pounds)	20 (40)	9 (18)	0.03	23 (46)	17 (34)	0.37
No weight change	24 (48)	29 (58)		16 (32)	15 (30)	
Weight gain $(> +3 \text{ pounds})$	6 (12)	12 (24)		11 (22)	18 (36)	

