### Table 1: Mean weight change by group CGM vs. SMBG (21)

Page 4 of 14

Figure 2: Representative Tracings of Patients with Prediabetes, Diabetes and Normal(24)

Normal mg/dl	PreDM mg/dl	T2DM mg/dl
+/- SD	+/- SD	+/- SD
100.0 +/- 16.4	119.9 +/- 25.5	141 +/- 41.8

Table 2: Average blood sugars of Patientswith Normal, Prediabetes, Diabetes (24)

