Title: A	Pilot Study on the Use of Real-Time Continuous G	ilucose Monitoring	(RT-CGM) as a	Tool for Weig	ht
Lo	ss/Behavior Modification in Patients with Prediab	etes and Diabetes			

NCT #: 03805412

Date: 18 November 2018

Initial statistical analysis

Sample Size Justification and data analysis: In order to establish stable estimates of effect sizes, we anticipate using a total sample size of N=30 patients (15 prediabetes, 15 Type 2 diabetes). Data will be analyzed using mixed model regression, which accounts for within subject correlation. The relevant effect size for each outcome will be the time main effect. As a secondary analysis, we plan to examine predictors of change using general linear models. This will help us determine the type of patient for whom the CGM intervention is most effective, which can inform the patient selection process in later studies. Predictors of interest include diagnosis (diabetes vs prediabetes), comorbidities, demographics (age, sex, race, type of insurance), BMI, and pre-intervention attitudes (toward diet, activity, and exercise changes)

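### The SAP's effect size for every outcome is one pooled time main effect, which does not compare the randomised arms and gives no change by diagnosis

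*SAP*

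**What the plan says.** The SAP (Sample Size Justification and data analysis) plans 30 patients, 15 with prediabetes and 15 with Type 2 diabetes, and a mixed model that allows for within-subject correlation. It lists no fixed effects apart from time: "The relevant effect size for each outcome will be the time main effect". A secondary analysis uses general linear models to look for predictors of change, and diagnosis heads the list: "Predictors of interest include diagnosis (diabetes vs prediabetes").

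The protocol (D. Research Design and Methods) describes 45 participants randomised to intervention or control: 15 prediabetes and 15 diabetes on intervention, 7 and 8 in control. Section I (Confidentiality) gives matching totals of 22 and 23. The eligible HbA1c ranges are 6.0-6.4% and 7.0-10%, so they do not overlap. Both arms receive the same lifestyle counselling at Week 2.

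The aims cover both diagnoses together. Aim 3 reads: "Evaluate the effect of RT-CGM on glycemic variability in subjects with prediabetes and diabetes".

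**The concern.** There are two gaps, of unequal weight.

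The larger one is that a time main effect is a before-after change. If only the 30 intervention patients are analysed, it mixes RT-CGM with the counselling that everyone receives. If all 45 are analysed, it averages over the arms. Neither version isolates the RT-CGM effect that the hypothesis is about.

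The smaller one is that a single figure per outcome averages two populations that the design keeps separate. If their changes differ, the average overstates one and understates the other. A reader interested in one diagnosis would find no planned estimate of that group's change and no interval for it.

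**Working it through.** **The plan's own figure.** The SAP gives no alpha, power, SD or precision target, so N = 30 cannot be derived. Only sums can be checked: 15 + 15 = 30 (SAP); 30 + 15 = 45 and 22 + 23 = 45 (protocol). The SAP's 30 equals the protocol's intervention arm and leaves out the 15 controls.

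**Why the arm contrast matters.** In the team's Type 2 study (C. Preliminary Studies), HbA1c at 12 weeks fell by 1.0% with RT-CGM and by 0.5% in the comparison group. A time effect in the RT-CGM arm would be -1.0. Averaged over arms at 2:1 it would be -(2 x 1.0 + 0.5)/3 = -0.83. The arm contrast is -1.0 + 0.5 = -0.5.

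**Could change differ by diagnosis?** The protocol cites a mean amplitude of glycemic excursion (MAGE) of 50 ± 18 mg/dL in prediabetes, and "excursions of 26-28 mg/dL in normal subjects and 75 +/- 28 mg/dL in patients with diabetes".
- MAGE gap to normal: 50 - (26 to 28) = 22 to 24 in prediabetes; 75 - (26 to 28) = 47 to 49 in diabetes.
- Mean glucose gap (Table 2): 119.9 - 100.0 = 19.9 against 141 - 100.0 = 41.0.

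Both gaps are about twice as large in diabetes. These are cross-sectional levels, not changes, and the MAGE values come from different sources.

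**What pooling would do.** The pooled change is the n-weighted mean of the two group changes. Take normal MAGE as 27 and assume that each group closes 20% of its gap:
- prediabetes: -0.20 x 23 = -4.6
- diabetes: -0.20 x 48 = -9.6
- pooled at 15:15: -7.1

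Then 7.1/4.6 = 1.54 and 7.1/9.6 = 0.74. At 40% the values double (-9.2, -19.2, -14.2) and the ratios stay the same. If instead both groups change by the same absolute amount, the pooled figure equals both.

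**Precision of the proposed reporting.** Units are the SD of change, assumed equal across groups. The 95% half-width is t/√n for one group and t√(1/n1 + 1/n2) for a difference.

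| Estimate | n | df | Half-width (SD) |
|---|---|---|---|
| Pooled change, intervention arm | 30 | 29 | 0.37 |
| Change in one diagnosis, intervention arm | 15 | 14 | 0.55 |
| Difference in change between diagnoses | 15 vs 15 | 28 | 0.75 |
| Arm-by-time, overall | 30 vs 15 | 41 | 0.64 |
| Arm difference, prediabetes | 15 vs 7 | 41 | 0.92 |
| Arm difference, diabetes | 15 vs 8 | 41 | 0.88 |
| Arm-by-diagnosis-by-time | all four cells | 41 | 1.28 |

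For the diagnosis difference at 15 vs 15 (two-sided 0.05, assumed), power is 26% at 0.5 SD and 75% at 1.0 SD. A difference of 1.06 SD is needed for 80%. These results are therefore useful as estimates and not as tests.

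**Weighting.** With assumed changes of 0 and -4, the pooled figure is -2.00 at 15:15 and (23 x -4)/45 = -2.04 at 22:23, so the planned split hardly matters. It would matter if diagnosis-specific variances were fitted without a three-way term. Using the MAGE SDs of 18 and 28 as stand-ins for SDs of change, the arm-contrast variances are 18² x (1/15 + 1/7) = 67.9 and 28² x (1/15 + 1/8) = 150.3. Inverse-variance weighting then gives prediabetes 150.3/(67.9 + 150.3) = 69%.

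**The case against.** The strongest reply is that the SAP already handles diagnosis. With one pre-post change score, a diagnosis term in a model of change is the same contrast as diagnosis-by-time, and that model also yields each group's fitted change. The aims are worded over both diagnoses, so a pooled average is a legitimate target. All of this stands. It reduces the diagnosis part to a request for pre-specified reporting. It does not answer the missing arm comparison.

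Several stronger readings are tempting but unsupported:

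- *The SAP ignores diagnosis.* It does not; diagnosis is the first listed predictor.
- *The pooled figure is what the SAP intends for planning later studies.* The SAP attaches that purpose to the secondary predictor analysis, which separates the diagnoses.
- *The pooled weight effect will be about half the diabetes effect.* This needs zero weight change in prediabetes. The earlier prediabetes study "did not show decreased glycemic variability or improvement in weight after 6 months", but the protocol suggests absent counselling and a demanding sensor schedule as reasons. Section B reports an average 4% weight loss across 28 translational prevention programs, though these were more intensive. Here both groups are obese and share the same counselling and 7% goal. The Type 2 weight result (40% vs 18% losing more than 3 lb by 12 weeks) is an arm contrast within diabetes, and at 52 weeks it was 46% vs 34% (P = 0.37).
- *Pooling biases the result or costs much precision.* At 15:15 the pooled estimate is the same with or without diagnosis-by-time. Leaving the term out inflates the SE by √(1 + d²/4), where d is the difference between diagnoses in SDs: 3% at d = 0.5 and 12% at d = 1.

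**Conclusion.** The point holds in two parts. First, the time main effect does not compare the randomised arms, and the SAP's sample leaves out the controls. This follows from the text alone and needs no assumption. Second, no change by diagnosis with a confidence interval is promised. This part is minor: it concerns interpretation, matters only if change differs by diagnosis, and is plausible mainly for glycemic outcomes. The 54% and 26% figures illustrate its possible size but rest wholly on assumed equal proportional closure of cross-sectional gaps.

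A reader might also infer that the primary model must carry diagnosis-specific variances and an arm-by-diagnosis-by-time term. The documents do not compel this. With control cells of 7 and 8 it is a debatable trade. For HbA1c with assumed SDs of 0.2 and 0.8, the equal-weighted arm contrast has SE ½√(0.2² x 0.2095 + 0.8² x 0.1917) = 0.18, where 0.2095 = 1/15 + 1/7 and 0.1917 = 1/15 + 1/8. Inverse-variance weighting gives 0.09, but for a mostly prediabetes average.

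**What to change.** 1. Bring the SAP into line with the randomised design: 45 participants, with arm-by-time as the primary effect in the mixed model.
2. Include diagnosis and diagnosis-by-time in that model as design factors.
3. Report change by diagnosis, and the arm difference within diagnosis, with 95% confidence intervals, labelled as descriptive estimates and not tests. The two-way model assumes one common arm effect, so take the within-diagnosis arm differences from separate summaries or a supportive fit.
4. Keep the secondary predictor analysis.
5. Optional for glycemic outcomes: diagnosis-specific variances or separate within-diagnosis summaries. If diagnosis-specific variances are used, state how the overall effect is weighted.

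The cost is a few degrees of freedom and some table rows; diagnosis is already collected. The drawback is imprecision, as tabulated above. With the 35% drop-out of the team's earlier pilot, taken only as a sensitivity value, about 9 per diagnosis would remain on intervention (15 x 0.65 = 9.75, rounded down) and the per-diagnosis half-width would grow to 0.77 SD. The text should say that a wide or null-spanning interval does not show equal change.

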GW Medical Faculty Associates Internal Medicine clinic, Gynecology clinic, and Endocrine clinic by medical staff and provider flier (Appendix F). Information about the study will be made available to those patients by a Study Flier (Appendix H) which will provide them with contact information for the study coordinator. As well, if potential participants express interest in the study to medical staff at GW, permission for the study coordinator to contact them via telephone or email will be requested and potential participants will be contacted for further screening and potential enrollment. The Study Screening and research procedures will take place at the GW endocrine clinic. Subjects may also be identified through posters and flyers placed in the GW community. Potential subjects who satisfy the study criteria and express interest in the study will be given information about participation either by mail, email or a phone call, depending on their preference. Pre-screening questions will be asked but no study related procedure or screening questions will be performed until informed consent/authorization have been obtained (see Appendices D and L).

We propose to perform a prospective study of 45 participants that will involve 15 subjects (ages 18-55) who are obese (BMI>30) and have prediabetes with HbA1c 6.0-6.4%, and 15 obese (BMI>30) subjects with Type 2 diabetes (ages 18-55) and with HbA1c 7.0-10.0%. 15 subjects will be in the control group with either prediabetes (n=7) or diabetes (n=8). Subjects will be randomized to intervention or control through a computer-generated system. All eligible participants will be able to walk 2 city blocks at baseline. Patients with prediabetes will be on no medications for diabetes and patients with Type 2 diabetes will have to be on the same diabetes medication(s) for 3 months prior to enrollment. The medication regimen may include basal insulin but not premeal insulin. Uncontrolled diabetes A1c>10.1% will be excluded, as well as participants who are pregnant, lactating, enrolled in another weight loss program, or using a weight loss medication (see inclusion /exclusion criteria below). The study will be advertised by flyers in the GW Endocrine Clinic, Internal Medicine Clinic, and also advertisements in the local newspaper.

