#### Weeks 2, 6

RT-CGM education and use will be coupled to one initial nutrition and exercise counseling session at Week 2 by the diabetes educator. Individually administered nutrition and exercise counseling will be based on a condensed version of the standard 12-session Diabetes Prevention Program Group Lifestyle Balance (DPP GLB, Appendix B) material and received by all participants. All those enrolled in the CGM intervention (N=30) will participate in 2 cycles of RT-CGM with direct feedback on CGM patterns at the second session, Week 2.

Both groups will then follow up and be given diet and exercise education handouts and instruction based on the DPP GLB core nutrtion and physical activity materials (Appendix B) at Week 2. The diabetes and prediabetes CGM intervention groups will also receive additional education on how food and exercise affects bloods sugar, and how to evaluate and respond to their blood sugar changes with RT-CGM (Appendix A). The CGM intervention participants will then wear the RT-CGM device for 10 days at week 2 and at 6 weeks. At week 2, CGM patterns will be reviewed with diet and food logs, and CGM intervention patients will be challenged "to beat their averages. The control group will review their diet and exercise log with the instructor and attempt to continue to make small changes in diet and exercise. Vital signs will be taken at each visit, including waist circumference. Pedometer data will be collected at weeks 6 and 14. Week 2 education on nutrition and RT-CGM will take 1 hour 30 minutes to 2 hours. Week 6 CGM review and measurements will take 1 hour. They will mail their sensors back from the continuous glucose monitoring device after 10 days, along with physical activity and food logs. They continue wearing their pedometers during this time.

Page 8 of 14

#### Week 14

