https://www.diabetesprevention.pitt.edu/index.php/for-the-public/for-health-providers/grouplifestyle-balance-curriculum. In this study, we will offer an adapted brief-intervention DPP in the first meeting. Our intent in providing this material is to support a primarily *self-directed* diet, activity and weight behavior modification context for use of the RT-CGM. Our diabetes educator will be responsible for reviewing the DPP materials and fat, calorie and activity goals at their original session along with materials developed about what different foods and activity does to your blood sugars prior to the initial use of RT-CGM. We reviewed the educational materials and handouts from the 12 sessions and consolidated them into a 12 page handout which was also reviewed by the current director of The Diabetes Prevention Support Center/DPP Lifestyle Resource Core at the University of Pittsburgh. Consistent with social cognitive theory, all participants are given fat and calorie goals based on their initial weight upon enrollment and an

Page 9 of 14

activity goal of 150 minutes of activity weekly with ongoing goal to 300 minutes weekly. They are asked to self–monitor weight, food intake and physical activity levels with goal of 7% weight loss (32).

**Measurements (Appendix C)**: We will measure HbA1c at the beginning of the study period and at 14 weeks. At each visit, blood pressure, weight, height, and waist circumference will be measured. At baseline and 14 weeks, questionnaires on diet and physical activity and selfperception questionnaires will be obtained. In the intervention group at 14 weeks, a questionnaire about CGM technology and perception of benefit of CGM use will be obtained, for diabetics and for prediabetics. Body composition will also be assessed serially by bioelectrical impedance using a Tanita scale at baseline and 6 weeks and 14 weeks. Pedometer data will be downloaded at 2 weeks, 6 weeks and 14 weeks. Physical fitness testing by resting heart rate and three minute stair step (amount of/change in steps climbed in 3 minutes) will also be obtained at baseline and 14 weeks.

**Anthropometrics: Height** will be recorded in centimeters and inches by a Stadiometer. **Weight** will be recorded in pounds and kilograms using a SECA Digital scale. **Waist circumference** will be meaured using a flexible measuring tape, and **blood pressure** taken with an Omron Professional Digital blood pressure machine.

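### The secondary analysis of predictors of change states no arm term or arm-by-predictor interaction, so it cannot show for whom CGM is most effective

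*SAP*

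**What the plan says.** The SAP is a single paragraph (Sample Size Justification and data analysis). It plans for 30 patients, 15 with prediabetes and 15 with Type 2 diabetes. For the main analysis it states: "The relevant effect size for each outcome will be the time main effect". The secondary analysis uses general linear models to look for predictors of change. Those named are diagnosis, comorbidities, demographics (age, sex, race, insurance type), BMI and pre-intervention attitudes. The stated purpose is: "This will help us determine the type of patient for whom the CGM intervention is most effective". The SAP adds that this can guide patient selection in later studies. Treatment arm is not among the predictors, and no interaction or control group is mentioned.

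The protocol describes a larger, controlled study. Research Design and Methods sets out 45 participants randomised to intervention or control, with 15 controls (7 prediabetes, 8 diabetes). Under Weeks 2, 6 it says: "All those enrolled in the CGM intervention (N=30) will participate in 2 cycles of RT-CGM". The same section describes the condensed Diabetes Prevention Program counselling as "material and received by all participants". Study Procedures says: "all participants are given fat and calorie goals based on their initial weight upon enrollment".

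The SAP does not say which arm its 30 patients come from. That they are the CGM arm is an inference from the matching total. No protocol section supplies an arm-based analysis of predictors.

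**The concern.** To ask for whom CGM works best is to ask whether the CGM-versus-control difference varies with a patient characteristic. That needs outcomes in controls and an arm-by-predictor term. The planned models ask only who changed most.

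Change here has an evident source other than CGM, since everyone receives the lifestyle counselling and calorie goals. BMI is especially exposed because those goals depend on initial weight. Heavier participants might lose more weight in both arms equally. The plan would then report BMI as marking the patients for whom CGM works, and a later trial could select on it.

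**Working it through.** **Inputs.** From the SAP: 30 patients (15 + 15). From the protocol: 30 CGM participants and 15 controls (7 + 8), total 45. The SAP justifies its size only in these terms: "In order to establish stable estimates of effect sizes". It gives no alpha, power, effect size or SD, so 30 cannot be re-derived; only the sum 15 + 15 = 30 can be checked, and it matches the CGM arm. Neither document gives an SD of change or a predictor-outcome correlation. What follows is therefore in SD units, under assumed correlations, two-sided 5% tests and no dropout.

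**Step 1: what each model estimates.** Let A = 1 for CGM and 0 for control, let x be a predictor, and let mean change = a + τA + βx + γAx.

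- The CGM effect at x is τ + γx, so the SAP's question concerns γ.
- CGM arm only: the slope on x estimates β + γ.
- All 45 without an interaction: the slope estimates about β + (30/45)γ = β + 0.67γ, taking x to have the same spread in both arms.
- All 45 with A, x and A×x: the interaction estimates γ.

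Neither of the first two isolates γ. If γ = 0 and β ≠ 0, both still give a non-zero slope.

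**Step 2: continuous predictor with no effect modification (γ = 0).** Simulated trials with x ~ N(0,1) and y = ρx + √(1−ρ²)e, the same ρ in both arms. Proportion with p<0.05 (an independent rerun agreed within about 1 percentage point):

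| ρ | 30 CGM only | 45 pooled, no interaction | Interaction, 30 + 15 |
|---|---|---|---|
| 0.1 | 8% | 10% | 5% |
| 0.2 | 18% | 26% | 5% |
| 0.3 | 36% | 53% | 5% |
| 0.4 | 61% | 80% | 5% |
| 0.5 | 83% | 95% | 5% |

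**Step 3: diagnosis, 15 v 15, with no effect modification.** Noncentral t, df 28, noncentrality d/√(1/15 + 1/15) = d/0.365. For the same difference in both arms of d = 0.25, 0.5, 0.75 or 1.0 SD, the CGM-only model flags diagnosis in 10%, 26%, 51% or 75% of trials. A separate simulation with a constant CGM effect of 0.3 SD gave 26% and 76% at d = 0.5 and 1.0; pooling 45 without arm gave 36% and 90%, and the interaction test about 5%.

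The rates in Steps 2 and 3 are ordinary power to find a predictor of change. They become errors only when the finding is read as CGM effectiveness.

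**Step 4: what the right analysis can deliver.** Arm-by-diagnosis SE = √(1/15 + 1/15 + 1/7 + 1/8) = √0.401 = 0.633 SD.

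- 95% CI half-width (t, df 41): 2.02 × 0.633 = 1.28 SD.
- Detectable at 80% power: (1.96 + 0.84) × 0.633 = 1.77 SD (normal), or 1.82 SD (t).
- Continuous predictor acting in the CGM arm only, ρ = 0.3, 0.4 or 0.5: interaction power about 15%, 24% or 37%.

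**Step 5: multiplicity.** If 8 to 10 independent null predictors were each tested at 5%, the chance of at least one p<0.05 is 1 − 0.95⁸ = 34% to 1 − 0.95¹⁰ = 40%.

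**The case against.** Several objections deserve an answer.

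- **It follows from a larger omission.** The SAP ignores the control arm throughout, and the secondary models inherit that. True, but adding an arm comparison to the main model would not repair the predictor models, which need their own interaction or different wording.
- **The wording is tentative.** The predictor list is not presented as exhaustive, and the claim is only that the analysis will help. So the accurate statement is that no arm term is stated, not that one is ruled out. But an unstated interaction is not pre-specified, and with 30 CGM participants alone no arm term could be fitted.
- **The arms differ by more than the device.** CGM participants also get extra education on food, exercise and blood sugar. This stands as a point of interpretation: the interaction would concern CGM plus that education, which is the CGM intervention the SAP names. It does not help separate prognosis from effect.
- **No significance test is planned.** The SAP sets no alpha here, so the flag rates and the multiplicity figure are illustrations. The bias in Step 1 (β + γ in place of γ) does not depend on testing.
- **The interaction is hopelessly imprecise.** Largely true, and dropout makes it worse. The protocol's Background reports 35% dropout in the team's earlier pilot of a different programme. Applied evenly here, the SE becomes 0.633/√0.65 = 0.79 SD and the detectable difference 2.8 × 0.79 = 2.2 SD. This argues for modest claims, not for a sharper estimate of another quantity.
- **Diagnosis is tied to medication.** Prediabetes participants take no diabetes drugs, while those with diabetes may. This stands as a caveat on any arm-by-diagnosis estimate.

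**Conclusion.** The point holds: the secondary analysis is wrong as written for its stated purpose. It can describe who changed most, but it cannot show for whom CGM is most effective. This is so on either reading of the analysis set, 30 CGM participants or 45 pooled without an interaction, and it does not depend on any assumed figure.

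The size of the risk does depend on assumptions. A purely prognostic predictor would be flagged in roughly 8% to 83% of trials with n=30 as its correlation with change goes from 0.1 to 0.5. The plan should be changed, but this is a secondary analysis in a pilot, and the defect does not touch study conduct or participant safety.

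**What to change.** **Preferred.** In all randomised participants, model change on arm, predictor and arm × predictor. Pre-specify one modifier of main interest; diagnosis is the natural candidate because the study is built around it. Report its interaction with a 95% CI as hypothesis-generating, noting the link with medication. Report the other predictors in the same form, labelled exploratory and without significance claims.

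**Minimum.** If models in CGM participants alone are kept, say explicitly which participants are included, describe the results as predictors of change among CGM users, and delete the statements about effectiveness and patient selection.

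**Cost.** A few sentences in the SAP and a few extra model fits on data already being collected. The drawback of the preferred option is the imprecision shown in Step 4, so only an exploratory estimate is realistic, and the SAP should say so. The minimum option needs no extra analysis, but gives up the question of who benefits from CGM.
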